8.3.1 Follow-up for Adverse Events

[name] or [name] will record all reportable events with start dates occurring any time after informed consent is obtained until 7 (for non-serious AEs) or 30 days (for SAEs) after the last day of study participation. At each study visit, the investigators will inquire about the occurrence of AE/SAEs since the last visit. Events will be followed for outcome information until resolution or stabilization.

8.4 Safety Monitoring

We will follow NIA guidelines for data monitoring procedures and have developed a data safety monitoring plan that will be reviewed and approved by an appointed Safety Officer, [name].

9 INTERVENTION DISCONTINUATION

There are no criteria for discontinuation at this point.

10 STATISTICAL CONSIDERATIONS

10.1 General Design Issues

This pilot project is not intended to identify specific outcomes resulting from the PPC approach, thus no power calculations are needed. We will use descriptive statistics to examine frequency distributions and proportions for all quantitative variables. We will calculate effect sizes for changes in our exploratory outcome. Interviews with practice-based implementation team members will be performed by [name] and analyzed using directed content analysis. Quantitative and qualitative findings will be triangulated using standard content analysis methods to create meta-themes that synthesize the quantitative and qualitative findings. Inclusion of 20 subjects is therefore sufficient to directed content analysis with the expectation that we will obtain data saturation of each content area.

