The primary objective of this pilot proposal is to adapt PPC for Hispanics. A secondary objective is to test the feasibility of using it on Hispanics with dementia. We will thus adapt and test PPC with 5 Hispanics and then test the adapted version with 20 Hispanics with dementia. One exploratory outcome is to determine if primary care providers use the identified priorities in the electronic medical record to guide changes in care aligned with priorities. The degree of alignment of care with priorities will be analyzed through chart reviews.

Interventions and Duration

Each participant will have one priority setting session with a PPC facilitator and one care alignment session with their PCP and will then have 1 interview with a research team member to evaluate the intervention.

Sample Size and Population

This pilot project is not intended to identify specific outcomes resulting from the PPC approach, thus no power calculations are needed. We will use descriptive statistics to examine frequency distributions and proportions for all quantitative variables. We will calculate effect sizes for changes in our exploratory outcome. Interviews with practice-based implementation team members will be performed by [name] and analyzed using directed content analysis. Quantitative and qualitative findings will be triangulated using standard content

analysis methods to create meta-themes that synthesize the quantitative and qualitative findings. Inclusion of 20 subjects is therefore sufficient to directed content analysis with the expectation that we will obtain data saturation of each content area.

STUDY TEAM ROSTER

Principal Investigator: **[name]**

[name]
[name]
[name]
[contact]
[contact]

Role: PPC Content expert. He will oversee all research activities at UTMB and conduct quality control activities to make sure that adaptation and implementation of the PPC approach is done appropriately.

Co-Investigators: **[name] PhD**

[name]
[name]
[name]
[contact]
[contact]

Role: He will oversee implementation of the study at UTMB and will serve as the facilitator for all priority setting encounters in the study.

Research Coordinator: **[name], MS**

[name]
[name]
[name]
[contact]
[contact]

PARTICIPATING STUDY SITES

Site Principal Investigator: **[name] PhD**

The University of Texas Medical Branch
Geriatrics Clinic

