- 4) The day of the session, the facilitator will use the PPC materials and identify the patient priorities and document them in the electronic health record. The visit will be audio recorded.
- 5) A research team member will schedule an appointment with the patient's primary care provider (PCP) within 2 weeks to conduct the alignment portion of the PPC approach (Steps two).
- 6) The primary care provider will discuss the patient priorities and the provider will align care to meet those priorities and document changes in care based on the discussion on the electronic health record (Step 3).
- 7) A research member will call the patient and assess their satisfaction with the PPC

approach 2 weeks after the visit with the primary care provider.

- 8) A research member will contact the primary care provider and assess their satisfaction with the PPC approach.
- 9) The PI, Co-PI and advisory team will review all the information and make adjustments to the protocol for the feasibility phase.
- 10) Steps 1-8 will be repeated with 20 Hispanic patients with dementia to test feasibility of the adapted PPC approach for Hispanics.

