11.2 Data Management

Data related to priorities identification and care alignment will be pulled from the electronic health record to evaluate the feasibility of the intervention.

We will use Redcap to conduct the patient and clinician evaluation of the PPC approach. These responses will be securely stored in the UTMB research server.

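### Does the content-saturation argument for 20 patients fail because only practice-team interviews are expressly sent to directed content analysis?

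*Combined protocol and SAP*

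**What the plan says.** The Précis (Sample Size and Population), protocol Section 10.1 and the SAP carry nearly the same paragraph. It declines a power calculation and plans descriptive statistics. It then names one interview source for qualitative analysis: "Interviews with practice-based implementation team members will be performed by [name] and analyzed using directed content analysis". Next it says that quantitative and qualitative findings will be triangulated by content-analysis methods into meta-themes. It ends with the sample size statement: "Inclusion of 20 subjects is therefore sufficient to directed content analysis with the expectation that we will obtain data saturation of each content area". Section 10.2 adds no further reason for 20.

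Elsewhere the 20 are patients. Section 4, step 10 reads "Steps 1-8 will be repeated with 20 Hispanic patients with dementia to test feasibility of the adapted PPC approach for Hispanics". Those patients generate qualitative or partly qualitative material at several points:

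- The priority-setting session in Section 4, step 4: "The visit will be audio recorded".
- One evaluation interview for each participant (Précis, Interventions and Duration): "will then have 1 interview with a research team member to evaluate the intervention".
- The follow-up call in Section 4, step 7: "A research member will call the patient and assess their satisfaction with the PPC" approach.
- The provider's evaluation in step 8: "A research member will contact the primary care provider and assess their satisfaction with the PPC approach".

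Section 11.2 names the tool for the patient and clinician evaluations: "We will use Redcap to conduct the patient and clinician evaluation of the PPC approach".

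**The concern.** Read literally, the paragraph moves from interviews with staff to a count of patients and joins them with a word of inference. Saturation depends on how many people are interviewed in the group being coded. Enrolling 20 patients does not fix the number of distinct clinic staff or providers: all the providers work in one clinic, and nothing stops several patients from sharing one.

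The participant evaluation is the source closest to the question of feasibility in Hispanics with dementia, yet no passage assigns it a qualitative method. Two things would be at stake. The plan's only stated reason for 20 would not support 20. And saturation could later be reported without saying in which group it was judged.

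**Working it through.** **Is there a figure to reproduce?** No. The documents give no alpha, power, effect size, precision target or saturation rule, so no formula returns 20. The check is mainly a reading of the text.

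**Step 1: what the 20 counts.** Patients in the feasibility phase (Précis; Section 4, step 10; Sections 5.1 and 5.2; SAP). This part of the concern is correct.

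**Step 2: what is expressly sent to directed content analysis.** Practice-team interviews only, number not stated. This is also correct, and it is the same in all three places.

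**Step 3: what the inference follows from.** The sentence immediately before the sample size statement is the triangulation sentence, not the one on staff interviews. Triangulation covers quantitative and qualitative findings without limiting them to staff, and it too uses content-analysis methods. The patients' sessions, chart documentation and evaluations can enter there. On that reading 20 is a relevant count, and what is missing is a list of sources.

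**Step 4: does the provider evaluation relate to 20?** Partly. Step 8 falls within the steps that step 10 repeats for the 20 patients. If it is done once per patient, the number of provider evaluations is tied to 20. The number of different providers is not.

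**Step 5: would interviewee numbers matter in principle?** Yes. Suppose a theme is held by a share p of a group and n members are interviewed independently. The chance of hearing it at least once is 1 − (1 − p)^n. The values of p, and every n except 20, are assumptions.

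| n | p = 5% | p = 10% | p = 20% |
|---|---|---|---|
| 3 | 0.14 | 0.27 | 0.49 |
| 5 | 0.23 | 0.41 | 0.67 |
| 8 | 0.34 | 0.57 | 0.83 |
| 20 | 0.64 | 0.88 | 0.99 |

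For example, at n = 20 and p = 10%, 1 − 0.9^20 = 0.88. The table shows why the group should be named when saturation is reported. It cannot size the gap, because the staff number is unknown and rewording the rationale would not alter it.

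**Step 6: do binomial intervals measure the problem?** No. Exact (Clopper-Pearson) 95% intervals with 20 respondents are:

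- 0/20: 0% to 16.8% (upper limit 1 − 0.025^(1/20))
- 10/20: 27.2% to 72.8%
- 16/20: 56.3% to 94.3%

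The arithmetic is right, but the intervals describe proportions among 20 patients treated as a random sample. They say nothing about a mismatch between staff interviews and a patient count, and an interval for a proportion is not a saturation criterion. The patients also come from a clinic roster after provider exclusions (Sections 4 and 5.3).

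**Step 7: what would differ if the sources were named?** The sample stays at 20. The frequencies, proportions and effect sizes stay the same. No test, threshold or stopping decision depends on the sentence.

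**The case for a change.** The best case for changing the plan is that a pilot may decline to justify its sample size, but a justification it does offer should fit its data. If the sentence was meant to cover participant interviews, then the content-analysis sentence leaves out its main source in three places. Recording is stated only for the priority-setting visit, so codable open answers from the follow-up call are not assured.

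The first part stands as a comment on drafting: the text does not say which sources are coded or how many interviews each has. The rest carries less weight. Nothing says that the satisfaction call has open items, so harm to its open content assumes data that may not exist. If such answers are collected, the triangulation sentence already takes them in. Requiring the call to be coded, with recording or structured notes and possible ethics review, would add work the sponsor did not plan, on the strength of one reading of an ambiguous sentence. A precision statement in Section 10.2 is a preference in a study that plans descriptive statistics only. Who answers the call when a patient lacks capacity is a separate matter, and step 7 names the patient as the person called.

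**Conclusion.** The wording gap is real, but no change to the plan follows. The rationale as written does not connect a patient count to the one interview group it names, and the number of staff interviewees is not given. This is missing detail that a competent analyst supplies in the report: the sources coded, the number of distinct interviewees in each, and the source to which any statement on saturation applies. The plan allows all of that as it stands.

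The consequence is limited to an unclear justification and, at worst, an unclear sentence on saturation in the results. This conclusion rests on two features of the plan: the quantitative analysis is descriptive, and no decision hangs on saturation. It also rests on reading the triangulation sentence as covering the patients' material, which the text permits but does not state. If that reading is wrong, 20 simply has no stated rationale. That would still not show 20 to be too few for a feasibility pilot.

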7.1 Description of Evaluations

7.1.1 Screening Evaluation

Consenting Procedure

Potential participants will be contacted over the phone by the research coordinator who will explain the project. A script will be available on Redcap for consent. Consenting will be performed once over the phone and verbal consent will be documented on the form. If the patient is deemed unable to consent in the pre-screening phase by the PCP or if they obtain a score less than 12 in the telephone version of the MoCA, a competent caregiver will be asked to consent and then the patient will provide assent.

Screening

The screening process will continue until all participants are included in the study.

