7.1.2 Enrollment, Baseline, and/or Randomization

Enrollment

Enrollment will occur on the first visit where healthcare goals are identified.

Baseline Assessments

The visit where healthcare goals are identified is considered the baseline assessment.

Randomization

There will be no randomization.

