7.1.3 Follow-up Visits

There will be one follow-up visit once healthcare goals are identified to conduct care alignment with the PCP. Once this step is completed there will be 1 follow-up call to evaluate the PPC process.

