7.1.4 Completion/Final Evaluation

The care alignment visit is considered the final visit.

8 **SAFETY ASSESSMENTS**

A participant is enrolled if he/she completes the care alignment visit. No adverse events are expected given that only goal setting and care alignment will be performed as part of routine clinical visits.

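### Enrolment is defined at two different visits, so it is unclear which stage the 20 counts, and patients who stop before care alignment can vanish from the feasibility result

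*Combined protocol and SAP*

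**What the plan says.** **Sample.** Section 10.1 gives no power calculation and supports the feasibility sample with one sentence: "Inclusion of 20 subjects is therefore sufficient to directed content analysis with the expectation that we will obtain data saturation of each content area". The Précis repeats it, and the SAP has it nearly word for word. Section 10.2 says that no sample size is required.

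**Enrolment.** Section 7.1.2: "Enrollment will occur on the first visit where healthcare goals are identified". Section 8, opening sentence: "A participant is enrolled if he/she completes the care alignment visit". The first visit is the priority-setting session. The care alignment visit with the primary care provider comes later; Section 4, step 5 aims for it within 2 weeks. On screening, Section 7.1.1 says "The screening process will continue until all participants are included in the study".

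**Evaluation.** Section 4, step 7 has the patient called about satisfaction with the PPC "approach 2 weeks after the visit with the primary care provider". Section 7.1.3 says of the alignment visit: "Once this step is completed there will be 1 follow-up call to evaluate the PPC process". Step 8 adds a provider contact, with no timing: "A research member will contact the primary care provider and assess their satisfaction with the PPC approach". Of the priority-setting session, step 4 says "The visit will be audio recorded".

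**Chart work.** Section 8.1 and the Metrics and Protocol Deviations paragraphs under Section 11.3 cover enrolled subjects. The monthly review in the Monitoring paragraph is not limited in that way, and Section 11.2 extracts data on both steps from the health record to judge feasibility. Section 8.3.1 records reportable events from consent onward.

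**The concern.** Testing feasibility in an outpatient clinic is part of the primary objective in Section 2.1 and the secondary objective in the Précis. Section 7 describes the whole intervention as two clinic visits and one call. Whether patients with dementia and their caregivers get from the first visit to the second is therefore central to what the pilot should report.

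The two enrolment sentences treat that transition differently. Under Section 7.1.2, a patient who sets priorities and then stops is an enrolled non-completer. Under Section 8, the same patient was never enrolled. Because no rule says which applies to the 20, the denominator could be settled after the data are seen. The Section 8 choice would remove from the count the patients for whom the process did not work.

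**Working it through.** **Step 1: the plan's own figure.** The 20 has no alpha, power, rate, precision target, dropout allowance or saturation criterion behind it. It can be neither reproduced nor shown to be wrong, and this check does not try.

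**Step 2: follow one patient who sets priorities and does not reach care alignment.**

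| Item | Enrolment per Section 7.1.2 | Enrolment per Section 8 |
|---|---|---|
| Enrolled? | Yes | No |
| Counts toward the 20, if the 20 are the enrolled? | Yes | No |
| In the chart reviews of enrolled subjects (8.1, Metrics, Protocol Deviations)? | Yes | No |
| Event recording from consent (8.3.1)? | Yes | Yes |
| Missed visit detectable (11.2, Monitoring)? | Yes | Possibly; neither text is limited to enrolled subjects |
| Patient evaluation call? | No, it follows alignment | No, it follows alignment |

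The last row is the same in both columns. The recorded session takes place before the patient stops, so it cannot hold the reason. The provider contact is not expressly tied to an alignment visit, and the implementation-team interviews could touch on the reason, but both would be second-hand.

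**Step 3: size for completion.** The documents give no completion rate, so c (the share of first-visit patients who complete alignment) is assumed at 70% to 90%.

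- 20 counted at the first visit: completers 20c, non-completers 20(1 − c).
- 20 counted at completion: starters 20/c, non-completers 20/c − 20.

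| c | Completers of 20 starters | Non-completers | Starters for 20 completers | Non-completers |
|---|---|---|---|---|
| 90% | 18 | 2 | 22.2 | 2.2 |
| 80% | 16 | 4 | 25 | 5 |
| 70% | 14 | 6 | 28.6 | 8.6 |

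Exact (Clopper-Pearson) 95% intervals at c = 80%, if recruitment runs to 20 completers:

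- Section 8 denominator: 20/20 = 100% (83% to 100%).
- First-visit denominator: 20/25 = 80% (59% to 93%). The 25 here is 20/0.8 and is unrelated to the 5 + 20 patients of the two phases.

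If recruitment instead ends at 20 starters:

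- Section 8 denominator: 16/16 = 100% (79% to 100%).
- First-visit denominator: 16/20 = 80% (56% to 94%).

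The 100% therefore appears whether or not patients who stop are replaced.

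**Step 4: size for the exploratory outcome in Section 10.3** (care changed because of the documented priorities). Let p₁ be the proportion with such a change among completers and p₀ the proportion among non-completers. The proportion among all with priorities set is c·p₁ + (1 − c)·p₀, so

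ratio of completer figure to all-starter figure = p₁ / [c·p₁ + (1 − c)·p₀].

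- If p₀ = 0, the ratio is 1/c: 1.11, 1.25 and 1.43 at 90%, 80% and 70%. For example, 15 patients with a change (an invented count) read 15/20 = 75% (51% to 91%) among completers and 15/25 = 60% (39% to 79%) among all with priorities set.
- If p₀ = p₁, the ratio is 1 and there is no inflation.

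**The case against.** The strongest reply is that the Section 8 sentence is a loosely worded safety-review population. It opens the safety section, and Section 8.3 looks for events after care alignment. No passage defines a completion rate with the enrolled as denominator. Section 11.2 and the monthly chart review would reveal a priorities note with no alignment visit. Replacement of patients who stop is nowhere stated: Section 7.1.1 says only that screening goes on until everyone is included.

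Much of this stands. Missed visits are detectable, and replacement is an inference. It does not remove the contradiction. Section 8 says when a participant is enrolled, not who is in a safety review, and other paragraphs use enrolment to define whose charts are reviewed. Read as a safety population, it also sits badly with Section 8.3.1, which starts from consent. Detecting a missed visit does not supply its reason.

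The reply is also right about the exploratory outcome. Section 11.1 puts the priorities in the record for providers, and Section 10.3 does not require the alignment visit, so a non-completer could still have a priority-driven change. The factor 1/c is an upper case that needs p₀ = 0.

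A reader might go further and infer that the justification of the 20 rests on the enrolment definitions, or that 20 patients cannot give saturation on why the process fails. The documents support neither. The saturation sentence is a bare expectation that invokes neither definition, and with no criterion stated no calculation can show 20 to be too few. It also directly follows text on implementation-team interviews, which could cover reasons for stopping. Failures after alignment, such as a visit that changed nothing, can be picked up by the call, the provider contact and the chart review.

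**Conclusion.** The point holds in a limited form. Sections 7.1.2 and 8 contradict each other on when a patient is enrolled, and nothing says which stage the 20 counts. Following Section 8 makes completion among the enrolled 100% by construction and takes patients who stop out of the chart reviews of enrolled subjects. Under either definition, no first-hand account from the patient or caregiver of why they stopped is planned.

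At an assumed 80% completion, the reported figure moves between 100% and 80%. The exploratory proportion shifts by at most a factor of 1.25 on the condition given in the working, and possibly not at all. Both sizes depend on a completion rate that the documents do not give. The contradiction and the timing of the call do not. This is not a finding that the sample is too small.

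**What to change.** 1. **One enrolment point.** Count enrolment, and the 20, from the priority-setting visit as in Section 7.1.2. Reword the opening of Section 8 to match, so that chart reviews of enrolled subjects include those who stop.
2. **Participant flow and denominators.** Report the numbers contacted, consented, with priorities set, with care alignment completed, and evaluated. Give completion and the Section 10.3 outcome out of all with priorities set, preferably with exact intervals, and the completer-only figure as secondary. Say so in the SAP.
3. **Reasons for stopping.** Offer the existing evaluation call, with one added item on the reason for stopping, to participants who do not reach alignment and have not withdrawn. Section 12.2 lets participants withdraw at any time, so some will not be reachable.

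The cost is wording in Sections 7.1.2, 7.1.3, 8, 10.1 and 10.3, in the matching Précis and SAP text, and in Section 4, step 7. Beyond that it needs a flow table, about 2 to 6 calls per 20 patients at 70% to 90% completion, and chart review for the same few patients. No extra clinic visit or larger sample is needed. The completion figure may come out lower than the one the Section 8 rule would give.
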